## SYNOPSIS OF RESEARCH CONTINUED

### **Introduction**

Cytomegalovirus (CMV) infection is the most common congenital infection worldwide and the leading cause of non-genetic sensorineural hearing loss (SNHL) in childhood. Prevalence of congenital CMV infection ranges from 0.6 to 5% dependent on the population studied. Up to 17% of all infected newborns are at risk of permanent neurologic sequelae, including SNHL; motor, cognitive and visual impairment; microcephaly; seizures and cerebral palsy. Morbidity data on congenital CMV infections has mostly been from high income countries (HIC). It is necessary to establish whether congenital CMV infection in South African children presents the same public health impact as in high resource countries and determine the effect of HIV on CMV infection.

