### 3.4 Objective 3, 6 (exploratory) and 7 (exploratory) Methods

[figure not shown]
***Study design:*** Prospective longitudinal cohort study of CMV infected and uninfected neonates

***Study participants:*** The cohort will consist of newborn infants identified as laboratory confirmed CMV infected from objective 2 forming the cases and a subset of neonates identified as CMV uninfected at birth chosen as controls. Each case will be matched to 2 controls by age, gestational age at birth ( $\pm 2$  weeks) and HIV exposure. Within 2 weeks of age, cases and controls will be recalled to the site to consent for follow up and initiation of investigations as illustrated in figure 2.

***Data collection:*** Postnatal CMV acquisition: A saliva and urine sample from each control infant will be collected at the 2 weeks visit. At subsequent follow up visits, infant saliva and urine will be collected from those that tested CMV negative at the preceding visit.

Incidence of neurological sequelae: neurological sequelae is one or more of: unilateral or bilateral SNHL, developmental deficit, unilateral or bilateral ocular abnormality, abnormal cerebral imaging, microcephaly, or seizures not related to an acute systemic infection or CNS insult (refer to [Appendix 11](#) for case definition of each sequela).

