Antibody to diphtheria toxoid, tetanus-toxoid, pertussis toxoid, filamentous hemagglutinin (FHA) and hepatitis B surface antigen (HBsAg) will be measured by an in-house Luminex multiplex immunoassay. Immune responses to the primary series of PCV will be measured by a standardized enzyme immunoassay (EIA) to test for vaccine serotype-specific capsular immunoglobulin (Ig) G antibody concentrations and opsonophagocytic assay. Titres of rotavirus-specific IgA will be determined in enzyme-linked immunosorbent assays. Refer to appendix 10 for the serological correlates of protection .

**Sample size:** The anticipated prevalence of neurological sequelae in CMV uninfected controls with uneventful foetal or perinatal periods is estimated at 1%. Prevalence of neurological sequelae in CMV infected infants is expected to be higher at approximately 17%. For 80% power, the difference that could feasibly be detected, is 17-fold i.e. 1% vs 17%. Allowing for a loss to follow up of 10%, 42 CMV infected infants and 84 controls (n=126) with an allocation ratio of 1:2 are required ([Appendix 9](#)).

**Data Analysis:** Table 3 describes the data analysis plan to determine the incidence and risk factors for neurological sequelae in congenital CMV infected infants

Table 3: Data analysis plan

Objective 3  Incidence calculation of one or more neurological sequelae for cases and controls at 2 weeks, 2 months, 6 months and 12 months of age dependent on investigations done at each visit  Comparison of proportions with permanent sequelae (hearing impairment and developmental deficit) at each visit between cases and controls using a Z test to compare ratios, including 95% confidence intervals.  Adjust for potential confounders (IUGR, symptoms at birth, gender and co-morbidities) by multiple logistic regression analysis to establish factors contributing to neurological sequelae.
Objective 6  Incidence of postnatal acquisition of CMV in newborns will be calculated at 2 months, 6 months and 1 year of chronological age. Incidence of neurological sequelae in postnatally infected infants will be calculated
Objective 7

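### Objective 3's multiple logistic regression has about 7 expected events for five terms, and its power statement is not tied to the outcome and visit that the named test covers

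*Combined protocol and SAP*

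**What the plan says.** Section 3.4 (Data collection) defines the outcome as a composite: "neurological sequelae is one or more of: unilateral or bilateral SNHL, developmental deficit, unilateral or bilateral ocular abnormality, abnormal cerebral imaging, microcephaly", or seizures without an acute cause. The Sample size paragraph uses the same term. For controls, "prevalence of neurological sequelae in CMV uninfected controls with uneventful foetal or perinatal periods is estimated at 1"%. For cases, "Prevalence of neurological sequelae in CMV infected infants is expected to be higher at approximately 17"%. It concludes "For 80% power, the difference that could feasibly be detected, is 17-fold i.e. 1% vs 17"%, and after 10% loss to follow-up asks for 42 infected infants and 84 controls.

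The Objective 3 entry in the section 3.4 analysis table has three parts:
- Incidence of the composite at 2 weeks, 2, 6 and 12 months, subject to which investigations each visit includes. No test is named.
- A test of two components only: "Comparison of proportions with permanent sequelae (hearing impairment and developmental deficit) at each visit between cases and controls using a Z test".
- An adjusted analysis: "Adjust for potential confounders (IUGR, symptoms at birth, gender and co-morbidities) by multiple logistic regression analysis", with neurological sequelae as its outcome.

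Section 2.1 gives Objective 3 a horizon of 12 months. Section 3.4 matches each case to two controls on age, gestational age and HIV exposure.

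**The concern.** Objective 3 is a primary objective, and its comparison of infected with uninfected infants raises two questions.

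First, the power statement and the named unadjusted test use different outcomes, and the test is repeated at up to four visits. A reader cannot tell which result the 80% refers to, or which would count as the main one if they disagreed.

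Second, the sizing rates imply very few events. An unpenalised logistic model with several terms can then give unstable or infinite coefficients, and the adjusted CMV odds ratio may not be estimable.

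**Working it through.** **Inputs.** Rates of 17% and 1%, 10% loss, 42 cases and 84 controls: section 3.4, Sample size. Four adjusters: section 3.4 analysis table. Symptom-specific rates: section 1.2. Two-sided 5% is assumed, because no significance level is stated for Objective 3. Control rates of 3% and 5% are also assumptions.

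**The plan's sample size.** For 17% vs 1%, 1:2 and 80% power, standard formulas give these numbers of cases before and after 10% loss: pooled 33 and 37; continuity-corrected 41 and 46; unpooled 45 and 50. None gives 42 after the allowance. The stated size is nevertheless adequate for the composite. At 38 vs 76 (42 × 0.9 and 84 × 0.9, rounded), pooled Z power is 85% by the normal approximation. By exact enumeration it is 92%, and Fisher's test gives 90%.

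**Alignment.** The Synopsis (Introduction) attaches the 17% to infants "at risk of permanent neurologic sequelae, including SNHL; motor, cognitive and visual impairment; microcephaly; seizures and cerebral palsy". That list is close to the section 3.4 composite, with abnormal cerebral imaging the clear addition. The named test covers hearing and development only. Section 1.2 allows a rough rate for hearing loss alone in infected infants:
- Low: 0.10 × 0.30 + 0.90 × 0.10 = 12.0%
- High: 0.15 × 0.60 + 0.85 × 0.10 = 17.5%

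Exact pooled Z power against 1% at 38 vs 76 is 77% and 93% respectively, if all of the loss shows by 12 months. The normal approximation gives 70% at 12%; with counts this small the exact figure is preferable. Power would be lower at earlier visits.

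**Expected events.**
- After loss: 38 × 0.17 + 76 × 0.01 = 6.46 + 0.76 = 7.2; 7.2 / 5 = 1.4 per term
- No loss: 42 × 0.17 + 84 × 0.01 = 7.14 + 0.84 = 8.0; 8.0 / 5 = 1.6 per term
- Case rate rebuilt from section 1.2: from 0.10 × 0.40 + 0.90 × 0.14 = 16.6% to 0.15 × 0.58 + 0.85 × 0.14 = 20.6%, or about 7.0 events (after loss) to 9.5 (no loss)
- Control rate 3% or 5%: 6.46 + 2.28 = 8.7 or 6.46 + 3.80 = 10.3 events, 1.7 or 2.1 per term

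The five terms are CMV status, which the table implies but does not list, and the four adjusters at one term each. If the model is fitted in infected infants only, it has 37.8 × 0.17 = 6.4 events for four terms, or 1.6 per term.

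**Chance of no control event among 76.** 0.99^76 = 47%; 0.97^76 = 10%; 0.95^76 = 2%. In that event the ordinary CMV odds ratio has no finite estimate. The same is true of a risk ratio, if that is what "using a Z test to compare ratios, including 95% confidence intervals" means. Read as a two-proportion Z test, that line is unaffected.

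**Other coefficients.** In simulation of the five-term model (2000 datasets per setting), at least one coefficient had no finite estimate in 60% to 88% of datasets at 1% controls and 33% to 76% at 3%. This counts any coefficient, not CMV alone. It rests on assumed prevalences: symptoms at birth in 0 to 10% of controls, IUGR and co-morbidity each in 10 to 30% of infants.

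**Control rate.** The 1% is for uneventful pregnancies and births, but controls are matched to cases on gestational age and HIV exposure, so it may be low. Exact pooled Z power at a 17% case rate is 92%, 73% and 54% for control rates of 1%, 3% and 5%. The case rates detectable with 80% power are 12.8%, 18.7% and 22.9%.

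**The case against.** The strongest reply is that the mismatch is mostly loose wording. The Synopsis and the analysis table both speak of permanent sequelae, and developmental deficit may cover the motor and cognitive items. Not every component need be examined at every visit, which would explain a narrower repeated test. The logistic model does take the composite as its outcome, so the composite has some inference. Much of this stands. A reader might infer that the narrower test forfeits the stated 80% power. The documents do not support that: hearing loss alone gives 77% to 93%, and adding developmental deficit cannot lower the case rate. Section 3.4 (Potential challenges) already discloses that sequelae may appear after 12 months.

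A second reply is that a missing CMV estimate is a threat mainly at the 1% control rate, which is itself open to doubt. That also stands: the 47% falls to 10% and 2% at 3% and 5%. The event count stays thin at every one of these rates.

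The text does not say whether the model is conventional, penalised or conditional, and it could be read as fitted in infected infants only. On that last reading the zero-control argument drops out, but the model is no better supported. The consultation with a biostatistician promised in section 3.3 does not fix the outcome or the method in advance.

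**Conclusion.** The point holds, and chiefly against the adjusted analysis. About 7.2 events (8.0 with no loss) cannot support a conventional five-term logistic model. At the plan's own control rate there is close to an even chance that the CMV odds ratio has no finite estimate. It would be wrong to infer that the estimate will usually be missing whatever the control rate, or to read the 60% to 88% as applying to the CMV coefficient. How often other coefficients fail depends on covariate prevalences that the documents do not give. The unadjusted Z test is adequate on the plan's rates.

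The outcome mismatch is a matter of alignment: the main outcome and visit need naming, and no power shortfall is demonstrated. Appendices 3, 9, 11 and 12 and Figure 2 are not in the text available and may state a time point or an order of outcomes, so confidence is medium. The point should be fixed before analysis.

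**What to change.** 1. Name cumulative incidence of the composite by 12 months, the outcome used for sizing, as the main comparison. Make hearing/developmental deficit and earlier visits secondary, and report imaging-only findings separately.
2. Test it with a pooled score (Z) or exact test, and report the risk difference with a score 95% interval. This stays defined with no control event: 6/38 vs 0/76 gives 15.8% (7.4% to 30.4%).
3. Replace the multiple logistic regression with Firth-penalised or exact logistic regression with few terms. Keep the four named adjusters in a penalised risk-factor model labelled exploratory. A Firth model with CMV status alone has about 96% interval coverage at 17% vs 1%, 3% or 5%, with power of 91%, 73% and 54%. With 6/38 vs 0/76 its odds ratio is 30.6 (3.4 to about 4000), so the risk difference should carry the result.
4. State the case rate detectable with 80% power at 38 vs 76 for control rates of 1%, 3% and 5%: about 13%, 19% and 23% (pooled Z; 3% and 5% are assumptions).

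The cost is analysis-plan wording and standard software options. The downsides are a less favourable stated detectable difference and exploratory status for the risk-factor results. Other sparse-data methods would also serve; what matters is naming one in advance.

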**Clinical significance and long term outcome of congenital CMV:** Most newborns with congenital CMV are asymptomatic at birth (85-90%). Of the 10-15% of symptomatic newborns clinical manifestations range from mild, non-specific findings to multi-organ system involvement. The most frequent signs are petechiae, jaundice and hepatosplenomegaly. Central nervous system (CNS) signs include microcephaly, hearing impairment, chorioretinitis and/or

optic atrophy and seizures. Of the symptomatic neonates, about 50% are small for gestational age, 33% are born prematurely and 5% die in the neonatal period.

Permanent neurological sequelae occurs in 40-58% of symptomatic and 14% of asymptomatic infants at birth. Children with symptomatic birth infection may have multiple neurological sequelae including SNHL (30-60%), cerebral palsy and mental retardation (50-80%) visual impairment (20-35%) and neurodevelopmental behaviour disorders (30-60%). The most common sequela in infants asymptomatic at birth are SNHL (10%) with other complications occurring at a lower frequency: motor deficits (5%) and chorioretinitis (2%).

**Effect of HIV:** An estimated 3% of congenital CMV infection occurs in HIV exposed infants compared to 1% in HIV unexposed infants. HIV infected infants have an even higher prevalence of congenital CMV (10.3%) as found in a French perinatal cohort. In this study, HIV and CMV co-infected newborns had a 3-fold greater risk of symptomatic congenital CMV infection at birth (23%) than HIV exposed but uninfected infants (6.7%). CMV co-infection may also contribute to HIV disease progression with increased risk of mortality and faster progression of CNS disease in survivors. However, the incidence of vertical CMV transmission in HIV infected women decreased following introduction of antiretroviral therapy (ART) during pregnancy.

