**Table 2: Maternal and newborn data of interest**

Maternal data	Newborn data
Demographic: age, race, and contact details	Demographic: date of birth, gender, race
Clinical data: antenatal care details, past obstetric history, parity, gestation at delivery, delivery details, co-morbidities, HIV status and CD4 count, ART use	Clinical: gestational age at birth, birthweight, head circumference, APGAR scores, HIV exposure, symptoms at birth, discharge or admission details

Newborn saliva samples will be collected by placing an Orocot swab in the mouth for at least 1 minute. All symptomatic neonates for congenital CMV infection ([Appendix 11](#)) will also be screened for other congenital infections which include syphilis, toxoplasmosis, rubella and herpes as is the standard of care at CHBAH.

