**Table 3: Data analysis plan**

Objective	Data Analysis
1. Determine the seroprevalence of Cytomegalovirus infection (CMV) in HIV infected and uninfected pregnant women attending CHBAH	Table of maternal demographic and clinical characteristics as proportions
	Maternal CMV seroprevalence expressed as a percentage stratified by HIV status (95% confidence interval)
	Chi square test to compare reactivations/recurrent infections determined by IgG avidity and IgM presence compared to latent infection stratified by HIV status
2. Compare the prevalence of and risk factors for congenital CMV infection in HIV exposed and unexposed newborns	Prevalence of congenital CMV infection in HIV exposed and unexposed infants expressed as a percentage with 95% confidence interval
	Multiple regression analysis to adjust for potential confounders: gender, gestational age at birth, birth weight, birth order, symptoms at birth
	In HIV exposed infants, chi square tests for association between: 

- Congenital CMV infection and maternal ART use

- Congenital CMV infection and severity of maternal immunosuppression (CD4+ count levels)

To explore the association between maternal CMV shedding in vaginal fluid and breast milk and the risk of congenital CMV infection assessed by quantitative CMV PCR.	Chi square test for association between vaginal CMV shedding and congenital CMV infection 

- Stratify by varying ranges of viral shedding (high, moderate, low – quantification to be determined)

- Stratify by HIV infection though will have low power for this

**Potential challenges:** Objective 1, 2 and 5: Mothers may be reluctant to be enrolled in a study for an infection which is unknown to them. To mitigate this, a patient information leaflet will be provided to improve understanding and includes the potential benefit to the infant should he/she

be diagnosed to have congenital CMV ([Appendix 7](#)). Training of researchers in effective communication will be conducted.

Objective 5: CMV viral shedding is cyclical, highest during primary infection; reactivation or reinfection which when occurs during pregnancy may be transmitted to the foetus. This study may be limited by the collection of samples after delivery at which point, viral shedding may have ceased since pregnancy.

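### Symptoms at birth are adjusted for as a confounder although the protocol describes them as manifestations of congenital CMV, so a case-versus-control model for Objective 3 would not give the total effect of CMV

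*Combined protocol and SAP*

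**What the plan says.** Section 3.4, data analysis table, Objective 3. After a Z-test comparison of cases and controls the plan states: "Adjust for potential confounders (IUGR, symptoms at birth, gender and co-morbidities) by multiple logistic regression analysis to establish factors contributing to neurological sequelae".

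Section 3.3, data analysis table, Objective 2, where congenital CMV is the outcome: "Multiple regression analysis to adjust for potential confounders: gender, gestational age at birth, birth weight, birth order, symptoms at birth".

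Section 1.2 describes what these symptoms are. It says of infected newborns: "Of the 10-15% of symptomatic newborns clinical manifestations range from mild, non-specific findings to multi-organ system involvement". It lists neurological signs at birth: "Central nervous system (CNS) signs include microcephaly, hearing impairment, chorioretinitis and/or", and the sentence goes on to optic atrophy and seizures. It also gives the prognosis: "Permanent neurological sequelae occurs in 40-58% of symptomatic and 14% of asymptomatic infants at birth". Section 3.3 speaks of "All symptomatic neonates for congenital CMV infection", with the definition in Appendix 11, so symptom status is itself defined with reference to CMV.

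The Objective 3 outcome in section 3.4 is one or more of "unilateral or bilateral SNHL, developmental deficit, unilateral or bilateral ocular abnormality, abnormal cerebral imaging, microcephaly, or seizures", the seizures being those not explained by acute systemic infection or CNS insult. Section 2.1 names symptomatic infection as a separate item to be compared between HIV-exposed and unexposed neonates.

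**The concern.** A confounder must not be a consequence of the exposure. On the protocol's own account symptoms at birth are caused by congenital CMV and carry a higher risk of sequelae, which makes them an intermediate step. Conditioning on them in a case-versus-control model removes the part of the CMV effect that runs through symptomatic disease, yet the result would be read as the adjusted effect of CMV. No passage says that a direct effect is wanted.

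There may also be overlap with the outcome. Microcephaly, hearing impairment, ocular signs and seizures at birth resemble components of the sequelae composite, and incidence is counted from the 2-week visit. An early sequela could then be adjusted for itself. How far this happens depends on Appendix 11, which is not in the text available.

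In Objective 2 the covariate comes after the outcome. A consequence of congenital CMV would be presented among its risk factors, although symptomatic infection is a result to be reported in its own right.

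**Working it through.** **Inputs from the documents.** Share of infected newborns symptomatic s = 10–15%; sequelae risk a = 40–58% if symptomatic and 14% if asymptomatic (section 1.2). Sequelae 1% in controls and about 17% in infected infants; 42 cases and 84 controls; 10% loss to follow-up (section 3.4).

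**Assumed.** The share of controls with symptoms at birth, for which the documents give no figure. Control risk is set at 1% whatever the symptom status.

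**1. The plan's own 17%.** p = s × a + (1 − s) × 0.14. At s = 0.10 and a = 0.40: 0.040 + 0.126 = 0.166, in line with the plan. Over the full ranges p is 0.166 to 0.206.

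**2. Total odds ratio.** [p/(1 − p)] / (0.01/0.99), shown in the table.

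**3. Symptom-adjusted odds ratio.** Logistic models with CMV and symptoms, no interaction, fitted to expected counts. With no symptomatic controls the symptom term is estimated from cases alone, so the CMV term is the contrast for asymptomatic infants: (0.14/0.86)/(0.01/0.99) = 16.1.

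| s, a | Total OR | 0% of controls symptomatic | 2% | 5% | 10% | Adjusted OR passes total at about |
|---|---|---|---|---|---|---|
| 10%, 40% | 19.7 | 16.1 | 17.2 | 18.6 | 20.6 | 8% |
| 10%, 58% | 22.3 | 16.1 | 18.5 | 21.5 | 25.8 | 6% |
| 15%, 40% | 21.6 | 16.1 | 17.2 | 18.7 | 20.9 | 12% |
| 15%, 58% | 25.7 | 16.1 | 18.6 | 21.8 | 26.6 | 9% |

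From 0 to 5% symptomatic controls the change runs from −37% to −4%. At 10%, letting the symptom odds ratio in controls vary from 1 to 8.5, it runs from −3% to +24%. Part of any change is non-collapsibility of the odds ratio rather than mediation.

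**4. Sequelae attributable to being symptomatic.** The excess over the asymptomatic risk, as a share of all expected case sequelae, is s × (a − 0.14)/p. Lowest: 0.10 × 0.26/0.166 = 16%. Highest: 0.15 × 0.44/0.206 = 32%.

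**5. Precision.** Expected events are 42 × 0.17 = 7.14 and 84 × 0.01 = 0.84, about 8 in all. The unadjusted odds ratio is (0.17/0.83)/(0.01/0.99) = 20.3, Wald 95% interval about 2.0 to 201. After 10% loss (38 and 76 infants) it is 1.8 to 226.

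**6. Objective 2.** At 2.9% against 1.0% the HIV odds ratio is (0.029/0.971)/(0.010/0.990) = 2.96. Adding symptoms leaves it at 2.96 if symptoms depend on CMV only. It becomes 2.53 to 2.88 if HIV exposure multiplies symptom rates by 1.5 to 2 with a background rate of 1–5% (both assumed). The planned 31 and 11 cases among 1077 each give (31/1046)/(11/1066) = 2.87, 95% interval 1.44 to 5.74.

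**The case against.** The strongest objection is that no CMV odds ratio is named anywhere. Section 3.4 introduces its table as covering incidence and risk factors in congenitally infected infants, and the regression is meant to find contributing factors. If it is fitted to cases only, there is no CMV term and symptoms at birth are a legitimate prognostic factor. This stands as a real ambiguity. The case-versus-control reading is still the more natural one: adjusting for confounders presupposes an exposure, the sentence directly follows the comparison of cases with controls, and Objective 3 in section 2.1 names that comparison. The plan should say which model it means.

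It can also be said that the practical effect is small. The Z test does not condition on symptoms, the shifts could not be detected with about 8 events, and the model will be imprecise whichever covariates it holds. All of that is true and limits the weight of the point. It does not make the label right. The Z test is also worded for hearing impairment and developmental deficit only; for the wider composite the logistic model is the only formal comparison described.

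A reader might infer that the adjustment must shrink the CMV effect. The documents do not support this. They give no symptom rate for controls, section 1.2 calls some findings mild and non-specific, and controls are matched on gestational age, so a low control rate is not assured.

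**Conclusion.** The point holds for a model that compares cases with controls: symptoms at birth are not a confounder on the protocol's own description, and the adjusted CMV odds ratio would not be the total effect. With up to 5% of controls symptomatic, the adjusted value is 16.1 to 21.8 against a total of 19.7 to 25.7. Above roughly 6 to 12%, depending on the case rates, the order reverses. The size and sign therefore rest on an assumed quantity. What is certain is that the estimate answers a different question from the one its label suggests.

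Three stronger readings should be resisted:

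- All sequelae in symptomatic cases (24–42% of the expected case total, s × a/p) might be counted as removed by the adjustment. That includes the 14% risk which asymptomatic cases also carry; the excess is 16–32%.
- IUGR might be called the same error. Section 1.2 says "Of the symptomatic neonates, about 50% are small for gestational age, 33% are born prematurely", so IUGR may result from CMV, but it can have other causes and the text does not settle the matter.
- Objective 3 or Objective 2 as a whole might be thought compromised. The unadjusted prevalences, incidences and Z test are untouched, and in Objective 2 the harm is mainly one of interpretation.

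This should be fixed because the correction is nearly free, not because it would visibly change the result.

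**What to change.** - **Objective 3:** state whether the logistic model compares cases with controls or is fitted within cases. Remove symptoms at birth from the case-versus-control model. Use them only in a separate within-case analysis of sequelae not already present at birth, labelled descriptive.
- **Objective 2:** remove symptoms at birth from the regression and report them as the symptomatic-infection outcome that section 2.1 names.
- **Optional and separate:** show the Objective 3 result with and without IUGR, and say how the matching factors (age, gestational age, HIV exposure) enter the model.

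The cost is a few lines of plan wording and no new data. The downside is one extra, imprecise analysis: 42 × 0.10 to 0.15 gives about 4 to 6 symptomatic cases, with about 2 to 4 sequelae (4.2 × 0.40 = 1.7; 6.3 × 0.58 = 3.7) before those present at birth are excluded.

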## 2.2 Exploratory objectives

5. To explore the association between maternal CMV shedding in vaginal fluid and breast milk and the risk of congenital CMV infection assessed by quantitative CMV PCR.
6. Determine the incidence of postnatal CMV acquisition, in infants not CMV infected at birth, and explore possible risk factors, including maternal HIV status and the magnitude of maternal CMV shedding in vaginal fluid and breast milk.
7. Explore differences in immune responses to the primary and booster series of vaccinations (DTaP-Hib/HepB, PCV rotavirus and measles vaccines) between congenital CMV cases, postnatally acquired CMV cases and non-CMV infected controls at 6, 12 and 13 months of age.

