**Figure 1: Data collection process for Objectives 1, 2 and 5**

All children with any clinical finding are referred to the neonatology department at CHBAH for clinical management as per standard of care. If a newborn PCR indicates CMV infection, the mother will be contacted telephonically to return to the site within two weeks of birth. At this visit the implications of the positive CMV result will be explained and additional consent for the continued follow up of the child (refer to [Appendix 7](#) for ICF and [Appendix 8](#) for schedule of study visits). Should consent be confirmed, a second saliva swab and a urine sample will be collected for PCR to confirm CMV infection. Babies that test CMV negative on both the second saliva swab and urine will not be enrolled as a case as the saliva positivity may be a result of CMV infected breast milk contamination. However, they will be referred for hearing screening as standard of care. Cases testing positive on both saliva and urine or urine alone will continue as cases for objective 3.

Mothers of CMV cases will have a vaginal swab and breast milk collected for quantitative PCR by a research nurse or the investigator. A subset of mothers that tested seropositive for CMV but gave birth to CMV uninfected neonates will also be recalled as controls for the case mothers in a

1:1 ratio, matched by HIV infection, for vaginal fluid and breast milk collection within 2 weeks of delivery.

**Sample size:** Objective 1: Assuming the estimated CMV prevalence is 86% in pregnant women 200 mothers will be needed to estimate the true value with a desired precision of 5% and confidence interval of 95%.

Objective 2: Prevalence of congenital CMV in HIV exposed neonates is 2.9% and in unexposed neonates is 1.0%. Thus, a total sample of 1662 neonates with 831 HIV exposed and 831 unexposed (1:1 ratio) for 80% power, are required to detect a 2.9 fold difference in CMV prevalence between the 2 groups. This will be increased to 2160 neonates, to accommodate objective 3, to determine clinical sequelae in CMV infected infants ([section 3.3.1, Sample size](#)). After adjusting for 10% being non-evaluable, 1077 HIV exposed (providing 31 CMV infected) and 1077 HIV unexposed infants (providing ~11 CMV cases) are required. Ranges of sample size estimates for varying CMV prevalences by HIV exposure are given in [Appendix 9](#).

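### Objective 6 measures postnatal CMV incidence only in controls matched to congenital cases on HIV exposure, so an unstratified figure depends on how controls were chosen if acquisition differs by HIV exposure

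*Combined protocol and SAP*

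**What the plan says.** Section 2.2 sets Objective 6 as: "Determine the incidence of postnatal CMV acquisition, in infants not CMV infected at birth, and explore possible risk factors, including maternal HIV status". The group of interest is therefore newborns without congenital infection, and maternal HIV is a named candidate risk factor.

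Section 3.4 obtains the data from the control arm of the follow-up cohort: "A saliva and urine sample from each control infant will be collected at the 2 weeks visit". Infants negative at one visit are resampled at the next. No follow-up of other CMV-negative newborns for acquisition is described.

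On selection, section 3.4 states "Each case will be matched to 2 controls by age, gestational age at birth"; the same sentence sets a tolerance of 2 weeks for gestational age and adds HIV exposure as a matching factor.

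The expected case mix is in section 3.3, Sample size, Objective 2: "1077 HIV exposed (providing 31 CMV infected) and 1077 HIV unexposed infants (providing ~11 CMV cases) are required".

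The Objective 6 row of the analysis table in section 3.4 reads: "Incidence of postnatal acquisition of CMV in newborns will be calculated at 2 months, 6 months and 1 year" of chronological age. It mentions no HIV stratum, weight, confidence interval or risk-factor method. The Objective 1 and 2 rows in section 3.3 do give results by HIV status.

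**The concern.** Matching on HIV exposure serves the case-control comparison in Objective 3. It also gives the controls the HIV mix of the congenital cases, and the plan expects congenital CMV to be 2.9 times as common in exposed newborns. The controls are thus not a representative sample of infants uninfected at birth, which is the group that Objective 6 describes.

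If acquisition by 12 months differs between exposed and unexposed infants, one proportion calculated over all controls partly reflects the selection rule. It could then be read as the incidence for Soweto infants, which it would not be. Matching on gestational age may shift the mix too, but the documents give no figure from which to size that.

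**Working it through.** **Inputs.** Congenital CMV prevalence 2.9% (exposed) and 1.0% (unexposed), and 1077 newborns per group: section 3.3, Sample size. 42 cases and 84 controls: section 3.4, Sample size. Maternal HIV prevalence 29.9%, a national figure: section 1.2. Consecutive sampling: section 3.3, Study design. The documents give no postnatal acquisition rates, so those used below are assumptions.

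**1. Reproduce the plan's case mix.** 1077 × 0.029 = 31.2 and 1077 × 0.010 = 10.8, total 42.0. This agrees with the plan.

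**2. HIV mix of the controls.**
- 1:1 screening: 2 × 31 = 62 exposed and 2 × 11 = 22 unexposed; 62/84 = 73.8% exposed.
- Consecutive screening of the same 2154 newborns at 29.9% prevalence: 2154 × 0.299 × 0.029 = 18.7 exposed cases and 2154 × 0.701 × 0.010 = 15.1 unexposed cases; 18.7/33.8 = 55.3% exposed, and the matched controls follow.

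**3. HIV mix of infants uninfected at birth.**
- 1:1 screened sample: (1077 − 31) / (1046 + 1066) = 1046/2112 = 49.5%.
- At 29.9% prevalence: 0.299 × 0.971 / (0.299 × 0.971 + 0.701 × 0.990) = 29.5%.

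**4. Error of an unweighted incidence** = (exposed share in controls − exposed share in target) × (incidence in exposed − incidence in unexposed).

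| Screening | Controls exposed | Target exposed | Excess (points) | Error for a 10 / 20 / 30-point difference |
|---|---|---|---|---|
| 1:1 | 73.8% | 49.5% (screened) | 24.3 | 2.4 / 4.9 / 7.3 |
| 1:1 | 73.8% | 29.5% (29.9% prevalence) | 44.3 | 4.4 / 8.9 / 13.3 |
| Consecutive | 55.3% | 29.5% | 25.8 | 2.6 / 5.2 / 7.7 |

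**5. Both directions, 1:1 screening.** At 60% in exposed and 40% in unexposed infants, the unweighted figure is 54.8%, against 49.9% (screened mix) or 45.9% (29.9% mix). With the rates reversed it is 45.2%, against 50.1% or 54.1%. With 40% in both groups all three are 40%.

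**6. Precision.** Take 62 exposed at 60% and 22 unexposed at 40%, so p(1 − p) = 0.24 in each group.
- Unweighted: 1.96 × √(0.548 × 0.452 / 84) = ±10.6 points.
- Standardised to 49.5%: 1.96 × √(0.24 × (0.495²/62 + 0.505²/22)) = ±12.0 points.
- Standardised to 29.5%: 1.96 × √(0.24 × (0.295²/62 + 0.705²/22)) = ±14.9 points. The weights are 0.295/0.738 = 0.40 per exposed control and 0.705/0.262 = 2.69 per unexposed control.
- Within strata at 50% incidence: about ±12 points (n = 62) and ±21 points (n = 22).

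**The case against.** The strongest replies, and what stands of each:

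- **The plan never says the incidence is pooled.** This is true; it is inferred from a row that gives one calculation and no strata. Objective 6 also promises to explore maternal HIV as a risk factor, which implies looking at acquisition by HIV status, and those HIV-specific figures are not distorted by matching on HIV. Section 3.2 refers to Appendix 3 for a summary of the analysis, and that appendix is not in the available text. The point is therefore about what an unstratified figure would mean, not proof that strata will be omitted.
- **With equal rates there is no bias from the HIV mix.** This stands. A reader might infer that the figure is certainly biased, or biased upwards. The documents support neither: they give no acquisition rates, and the sign reverses if exposed infants acquire CMV less often.
- **Consecutive sampling lowers the exposed share.** This stands in part. The share of controls exposed falls from about 74% to 55%, still above 29.5%.
- **Matching is appropriate for Objective 3, and Objective 6 is exploratory.** Both stand. The matching needs no change, and the point is minor.

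A reader might also infer that the same error passes into the planned incidence of sequelae among postnatally infected infants. That needs a further condition, that the risk of sequelae among the infected differs by HIV exposure or gestational age, and nothing in the documents establishes it.

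**Conclusion.** The point holds in conditional form. The infants tested for acquisition are selected to resemble the congenital cases, so an unstratified incidence describes a matched cohort and not infants uninfected at birth in general. For an assumed 20-point difference by HIV exposure the discrepancy is about 5 points (1:1 screened mix), 9 points (29.9% mix after 1:1 screening) or 5 points (consecutive sampling), in either direction.

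This rests on the plan's congenital prevalences, on full 2:1 matching, on the national 29.9% figure standing in for Soweto, and on assumed acquisition rates. It is a low-severity improvement to an exploratory analysis.

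**What to change.** Amend the Objective 6 row in section 3.4 as follows:

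1. Report incidence at 2, 6 and 12 months separately for HIV-exposed and HIV-unexposed infants, with 95% CIs.
2. If an overall figure is given, standardise it to the HIV-exposure mix of a named target population, with a CI that reflects the weights. Use the screened CMV-negative newborns if screening is consecutive. If screening is balanced 1:1 by design, use the birth population, because the screened mix is then itself set by the design.
3. Label any unweighted figure as describing the matched control cohort only.

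Standardising for gestational age as well is optional: 84 infants split by HIV exposure and gestation would leave sparse cells.

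The cost is small. Table 2 in section 3.3 already lists HIV exposure for screened newborns, so no extra infants, visits or samples are needed. The loss is in precision: in the 60%/40% example the overall CI half-width goes from about 11 points to 12 (1:1 screened mix) or 15 (30% mix). The unexposed stratum, with about 22 infants, will be imprecise whichever way the results are presented.
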